6.3. Randomisation

Following completion of baseline information collection, a member of the research team will randomise the participant to one of the two treatment arms: physicist consultation or standard of care.

Patients will be randomised in order to minimise systematic bias, using a secure web-based system Sealed Envelope (https://www.sealedenvelope.com/simple- randomiser/v1/trials/rapport), certified as meeting ISO/IEC 27001 standards and the NHS England Data Security and Protection Toolkit.

Participants will be allocated to intervention group or to the control group in a 1:1 ratio. Randomisation will be stratified by gender. This is a surrogate for treatment site: the most common radiotherapy treatment sites (particularly at RWRC) are breast and prostate cancer. However, to ensure approximately equal distribution of treatment sites in each arm and avoid problems of low numbers of less common treatment sites, gender has been chosen has the stratification criteria. It is acknowledged that with the low sample size required in this study, distribution is likely still to be unequal but there is little evidence that the primary outcome varies by gender.

Upon randomisation, each participant will be assigned a unique Trial Number which will be used as the principal identifier on trial data collection forms and questionnaires. The research team member will disclose the allocation to the participant and will ensure the allocation is followed as described below.

6.4. **Provision of Treatment**

Following allocation, the participant will be informed of which trial arm they have been randomised to. Where required, the consultation will be booked by the PI or delegate and the patient informed what time this will be (as it will not be on their routine appointment list given at the CT appointment). If possible, a reminder will be sent via the DoctorDoctor service.

6.5. Start of treatment

When patients start treatment, they will be asked to complete a questionnaire on the day of their first treatment. Ideally this will be completed before the treatment appointment, otherwise it must be completed after the treatment appointment and on the day of first treatment. This is due to some patients having very short treatment regimens. Patients will be provided with a questionnaire packet to be completed, and a member of the research team will complete a case report form (CRF). The start of treatment data collected (either participant-reported or medical records) will be:

- Patient-reported anxiety STAIS6 questionnaire
- EQ-5D-5L questionnaire

- Technical satisfaction questions
- Clinical information collected from medical records
 - Scheduled number of treatment fractions (this can change between referral and prescribing by Oncologist)
 - Does the patient have bladder filling/preparation. If so, baseline volume and details from planning CT
- Intervention information (where applicable):
 - Physicist conducting consultation.
 - Consultation duration.
 - Discussion points and patient questions analysis of themes and topics will be conducted.

6.6. End of treatment

The time between the start and end of treatment clinic visit will be patient-specific, according to their radiotherapy treatment prescription. It is anticipated that it will be between 5 days and 6 weeks after the first treatment. The patient will be given a questionnaire to complete and a member of the research team will complete a CRF. Ideally the participant will be complete the questionnaire before their last treatment appointment, but it must be completed on that day. The end of treatment data collected (either participant-reported or medical records) will be:

- Patient-reported anxiety STAIS6 questionnaire
- EQ-5D-5L questionnaire
- Technical satisfaction questions
- Information and communication needs
- Questionnaire regarding physicist intervention (where applicable)
- Clinical information collected from medical records:
 - Where applicable: bladder prep information (to include volume at CT, volume each fraction, delays or incorrect prep)
 - Imaging data (to include 2D shifts, CBCT shifts where applicable)
 - SGRT data
- PPI free-text comments on the participants experience, the intervention, thoughts on a future clinical service etc.

6.7. End of Study

The end of the study is defined as the last day of radiotherapy of the last participant. The end of study declaration form will be completed after this date (and within 90 days) once all required data is present and the database is locked.

7. INTERVENTION DETAILS

7.1. Rationale, risks & benefits

Anxiety in radiotherapy patients is a known and common occurrence, with evidence around the negative consequences on health and outcomes it can have for cancer patients. Interventions to reduce this and improve quality of life (QoL) are a continued focus of research in the literature and novel approaches such as utilising medical physicists have

shown some benefit for reduced anxiety in the US. To date, there is no research demonstrating benefit from similar interventions in the UK (noting the substantially different healthcare systems and demographics). This research aims to establish whether a reduction in anxiety is observed in radiotherapy patients for a physicist-based education intervention. Additionally, the research will examine correlations between radiotherapy treatment shifts and patient-reported anxiety. Accurate setup is essential for effective treatment, and this may provide evidence to further embed anxiety interventions in standard practice for radiotherapy, ensuring patient-centred care is a leading priority in research and practice.

7.2. Assessment and management of risk

There are no known risks regarding the provision of information, with no adverse events reported in literature or regulating bodies. It is possible that additional information about the technical aspects of their treatment will have the unintended consequence of increasing anxiety. This will not impact the safety or efficacy of their radiotherapy treatment, and further support regarding anxiety via the routine radiotherapy patient review pathways will be available. Patients on the trial will be able to access complimentary therapies in the same way as standard of care patients.

The STAI, as discussed, is a widely validated tool that has lots of published evidence regarding its utility. However, it is still not widely adopted as a clinical screening tool, particularly in this cohort of patients. In normal populations a cut-off score of 40 (STAI manual) is used to indicate clinically significant symptoms of anxiety. However, it is expected that anxiety in cancer patients undergoing a procedure or treatment will be higher than that encountered in a normal population. There is little published population data on state (or situational) anxiety scores, but a recent paper examining anxiety in radiotherapy patients during the Covid-19 pandemic demonstrated the majority of patients had STAI scores $\geq 40^{64}$. Additionally, patient-reported anxiety is the primary outcome measure of the study (and correlation with it the secondary outcome measure). Directing patients to additional help during their treatment and highlighting high anxiety scores may bias the outcome. To counter these difficulties and ensure patients are as well-supported as possible, an information leaflet will be provided to all participants at the start of treatment detailing the support available developed in conjunction with the RWRC review radiographer/Macmillan lead.

It is acknowledged that radiotherapy physicists undertaking a more patient-facing role could be considered a risk. Any physicist undertaking the intervention is required to complete additional communication training (a uniquely tailored course developed by Atwood et al. who were one of the first to explore this expanded role for physicists⁶⁵.

7.3. Patient-Physicist Consultation

Medical physicists in radiotherapy do not undertake patient consultations as part of standard care, although they are done on an-hoc basis at a patients request. Any physicist undertaking the intervention must be documented on the delegation log and must have completed suitable training (as determined by the PI) in patient communication, and the intervention itself. The intervention will be conducted in line with a standard of practice (SOP), available to physicists undertaking the intervention to ensure consistency. The scope of the technical consultation is outlined below but will be driven by individual patient requirements and questions.

Typical discussion sequence during a medical physics consultation:

i	To give an overview of the role of the medical physicist (and other technical staff) in patient care
ii	Explain the CT simulation and treatment planning process
iii	Explain the treatment delivery process
iv	Overview of what to expect in the treatment room
v	Patient questions

It will be made clear to participants that non-technical and clinical questions, for example about side effects or medication, cannot be answered by the medical physicist and, where appropriate, questions will be passed onto relevant staff.

The intervention will take place on the patients' first day of treatment, ideally face-to-face. In circumstances where this is not possible, then a virtual consultation is permissible. This will be conducted via UHD Microsoft Teams, with staff at RWRC assisting the participant to ensure they have access to an appropriate device.

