The project is funded by Health Education England, as part of the doctoral component of the Higher Specialist Scientist Training (HSST), conducted through the National School of Healthcare Science (NSHCS) and the University of Manchester (UoM) as the academic awarding body.

vii. ROLES & RESPONISBILITIES OF TRIAL MANAGEMENT COMMITTEES / GROUPS

The Trial Management Group (TMG) chaired by the Chief Investigator, will include the research academic and workplace supervisors, a representative of the sponsor, and any other relevant local staff involved with the study. The TMG will take responsibility for monitoring progress, ensuring development of documentation and forms, monitoring participant recruitment, discussing analysis, results, draft reports and dissemination. The TMG will meet every 3 months.

viii. PROTOCOL CONTRIBUTORS

The sponsor (University Hospitals Dorset NHS Foundation Trust) and Chief Investigator are responsible for the trial design, conduct, data analysis and interpretation, manuscript writing, and dissemination of results. The funder (NHS England) does not have any control over aspects of the trial. Input from the research academic and workplace supervisors is also recognised ([name] & [name] respectively). Statistical advice on the trial sample size was sought from [name] (Bournemouth University).

Patient and public involvement (PPI) has been sought via patients undergoing radiotherapy at the Dorset Cancer Centre. A short questionnaire was distributed to patient waiting rooms at both the Poole and Dorchester radiotherapy departments. Most patients indicated they would say yes to an additional appointment with a medical physicist to address technical aspects of their treatment, and this response was independent of whether the patient had initial anxiety or worries about technical aspects of their treatment. An advert for patient advocates for the trial was made through this questionnaire. 1 patient responded and provided feedback on general aspects of their treatment, but no comments on the research proposed. Ad-hoc patient-physicist consultations done prior to this research proposal have been extremely well received, in particular allowing one patient to tolerate their treatment successfully when they were struggling. Another patient commented that they sincerely hoped these consultations would be something offered to patients regularly.

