2.2. Objectives

2.2.1. Primary objective

• To determine if an additional patient consultation with a medical physicist influences patient-reported anxiety compared to standard of care (no consultation with a medical physicist).

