3.2. Design and bias considerations

The nature of the intervention makes it impossible to blind the patient or staff. However, data analysis will be undertaken on a pseudonymised basis. Participant selection bias will be present, with those patients wanting to know more self-selecting. It is not possible to account for this, however statistical analysis will be stratified by education and health literacy level (as well other sociodemographic data).

Figure 2: Study design flowchart

Illustrating flow of patients through the trial and the time points for data collection (3 time points numbered)

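### Control is defined as having no physicist consultation, but these occur ad hoc on request; the protocol does not explicitly require recording them in controls, and groups the analysis by receipt

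*Protocol*

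**What the plan says.** **Comparator.** The primary objective (2.2.1) tests the consultation "compared to standard of care (no consultation with a medical physicist").

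**Usual practice.** Section 7.3 says that physicist consultations are not part of standard care, "although they are done on an-hoc basis at a patients request". The Protocol Contributors section adds: "Ad-hoc patient-physicist consultations done prior to this research proposal have been extremely well received". It describes two patients and gives no count.

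**Who the controls are.** Section 3.2 says "Participant selection bias will be present, with those patients wanting to know more self-selecting", and also "The nature of the intervention makes it impossible to blind the patient or staff". Under 6.3 and 6.4 participants are told their allocation. Section 3.3 expects about two weeks from consent and baseline to first treatment, then 5 days to 6 weeks to the last.

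**What is recorded.** At the start of treatment (6.5), the physicist's identity, the duration and the discussion points sit under "Intervention information (where applicable"). At the end of treatment (6.6) there is a questionnaire on the physicist intervention, again only where applicable. Table 2 schedules questions about the consultation at the end of the study. Section 8.4 undertakes to collect staff time on consultations without naming an arm.

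**Analysis groups.** Section 8.2 says the data are analysed by intervention group and explains this in brackets as those who had the additional consultation and those who did not.

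**The concern.** The comparator wording and the description of local practice do not quite match. A control participant who asks for a physicist may, under existing practice, be given something close to the intervention. Such requests are plausible: allocation is known, participants are expected to want more information, and the department has met requests before.

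Two things would then be at stake. First, if the contact is not recorded, a small or null difference could mean that the consultation has little effect or that some controls also had one. Nothing collected later could separate the two, and an SAP cannot recover exposure that was never captured. Second, if the contact is recorded, the grouping in 8.2 taken literally moves that patient out of the control group. The comparison then stops being randomised, and the patients who move are those who asked for help.

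**Working it through.** **1. Reading the sections together**

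- 2.2.1 against 7.3: both treat the consultation as outside standard care. They differ on the exception: 2.2.1 allows for none, while 7.3 says consultations happen on request.
- 6.3 says staff will see that the allocation is followed, but the text it points to (6.4) covers only telling participants their arm and booking the consultation. It does not deal with a request from a control participant.
- 6.5, 6.6 and Table 2 do contain consultation items. They are worded around the trial intervention. None explicitly asks about physicist contact outside it, in either arm.
- 8.2 needs receipt to be known in both arms before its grouping can be applied.

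The consequence under 8.2 as worded depends on recording:

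| Control who has an ad hoc consultation | Group under 8.2 | Effect |
|---|---|---|
| Recorded | Leaves the control group | Comparison no longer by randomisation; direction of bias unknown |
| Not recorded | Stays in the control group | Difference diluted |

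**2. The plan's own sample size**

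Inputs from 8.1: difference 10, SD 13, two-sided 0.05, power 80%, equal groups.

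n per arm = 2 × (1.960 + 0.842)² × 13² / 10² = 2 × 7.849 × 1.69 = 26.5, so 27 per arm and 54 in total. Allowing 10%: 54 / 0.9 = 60. Both figures reproduce. The 10% is for non-response, missing data and attrition, with nothing for crossover.

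The non-central t gives 79.2% power at 27 per arm (the normal approximation gives 80.7%) and 83.4% at 30 per arm. The non-central t is used below.

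**3. Dilution if crossovers stay in the control group**

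The documents give no crossover rate c, so the range below is an assumption. A crossover is assumed to gain the full 10 points, so the expected difference is 10 × (1 − c). SD is held at 13.

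Non-centrality = difference / (13 × √(2/n)). The denominator is 3.538 for n = 27 (52 df) and 3.357 for n = 30 (58 df).

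| c | Difference | Non-centrality, n = 27 | Power, n = 27 | Non-centrality, n = 30 | Power, n = 30 |
|---|---|---|---|---|---|
| 0 | 10 | 2.826 | 79.2% | 2.979 | 83.4% |
| 10% | 9 | 2.544 | 70.4% | 2.681 | 75.1% |
| 20% | 8 | 2.261 | 60.2% | 2.383 | 64.9% |
| 30% | 7 | 1.978 | 49.3% | 2.085 | 53.6% |

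Full benefit is the upper bound on dilution at a given c. If a crossover gains only a fraction f of the effect, the difference is 10 × (1 − f·c). For example, half benefit at 20% crossover gives 9 points, the same as the 10% row. Holding the SD at 13 is slightly favourable. Letting the control variance grow by 10² × c(1 − c) and pooling takes the 27-per-arm figures to 69.3% at 10% and 58.3% at 20%.

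**4. Timing**

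Contact before the first-treatment questionnaire can affect both follow-up scores. Contact after it can affect only the end-of-treatment score, which has a further 5 days to 6 weeks of exposure.

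**The case against.** The strongest reply is that 7.3 opens by saying physicists do not consult patients as standard care, so 2.2.1 and 7.3 agree on the main point and ad hoc contact is an exception. One of the two patients described hoped the service would be offered regularly, which suggests that it is not now. If requests are rare, randomised consultation against usual care is still a sound pragmatic comparison. This stands. A reader might infer that usual care routinely supplies a consultation, or that the trial cannot answer its question. The documents support neither.

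A reader might also infer that nothing about physicist contact is collected at the end of treatment. That is wrong: 6.6 and Table 2 both list questions on the consultation. The phrase about applicability is not expressly limited to the intervention arm, and the case report forms are not at hand. What can be said is that the protocol does not explicitly require non-trial contact to be recorded in controls.

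The power figures are also open to challenge. No crossover rate has a source, and full benefit is generous: the trial consultation follows an SOP, is given by trained, delegated physicists and precedes first treatment, whereas nothing says that ad hoc contact matches this. Both points stand, so the table shows sensitivity and does not predict the trial's power.

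Finally, the choice of a sensitivity estimate is ordinary SAP content. That is accepted. The comparator wording, the data items and the grouping sentence are fixed in the protocol.

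**Conclusion.** The concern holds in a limited form. The protocol defines control as no physicist consultation, acknowledges that such consultations occur on request, does not say how a control's request is handled, and does not explicitly require the contact to be recorded. With the grouping in 8.2, a recorded crossover loses its randomised place and an unrecorded one dilutes the difference.

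The size is unknown. Each 10% of controls who cross over with full benefit takes 1 point off the 10-point difference and roughly 8 to 11 percentage points off power over the range shown. This rests on the inputs in 8.1, an assumed crossover rate, full benefit, and analysis with crossovers left among the controls. The true rate may be low, but unless contact is recorded in both arms the trial could not show that. The point is worth acting on because the remedy is cheap and the missing information cannot be recovered later.

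**What to change.** 1. Reconcile 2.2.1 with 7.3. For example, state the comparator as usual care, in which physicist contact occurs only ad hoc on request. The sponsor should state how requests from control participants are handled during the trial.
2. Add one item to the 6.5 and 6.6 data collection for both arms: any physicist contact outside the trial consultation (yes/no, date, duration).
3. Reword 8.2 so that the primary comparison is by randomised group, with the number of crossovers reported per arm. This should accompany item 2, because recording crossovers under the present wording would invite moving patients between groups.

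The form of any sensitivity estimate can be left to the SAP.

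Cost: a wording amendment, one extra question at two existing visits, and a slightly less clean statement of the comparator.

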8. STATISTICS AND DATA ANALYSIS

8.1. Sample size calculation

Advice on the sample size calculation has been sought from [name], Principal academic in healthcare statistics at Bournemouth University.

The study is powered to detect a 10-point difference in patient-reported anxiety on the STAI. There is evidence that this is the minimally important difference (MID)^{18,42,66}. An estimate of standard deviation was made from work by Burmeister⁴² and Atwood³⁶ in similar radiotherapy populations, both studies used the STAI to measure patient anxiety. Atwood found standard deviations ranging from 10.2-15.6, whilst Burmeister found a lower standard deviation of 8.1. A standard deviation of 13 has been chosen to represent an average within the range of observed values from Atwood.

Based on an unpaired t-test with two groups of equal size, assuming 80% power, a twosided 0.05 significance level, a standard deviation of 13 and a mean difference of 10 points in patient-reported anxiety, a total sample size of 54 (27 in each group) is required. The study will over-recruit by 10% to allow for non-responders, missing data, or attrition (dropout). Therefore, the study will aim to recruit 60 patients in total (30 in each group) over a 1year recruitment period. This gives a similar sample size to the work of Atwood, and a sample size 1.5 times larger than Burmeister.

This sample size is also in the region of that calculated by an independent method (using the varying-slope varying-intercept model). Whilst this doesn't consider the repeated timepoints as independent, it represents a worst-case scenario. The details of this calculation are in Appendix 1, but the calculated sample size is 76 (although this doesn't account for attrition), slightly larger than the sample size calculated but of the same magnitude.

8.2. Description of statistical methods

A detailed statistical analysis plan will be developed and signed off by the Trial Management Committee before any analyses commence. The pseudonymised data will be analysed by intervention group (i.e. patients who did or did not receive the additional consultation).

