4.1. Primary outcome measure

The primary outcome measure for this study is patient-reported anxiety utilising a short form of the state scale of the Spielberger State-Trait Anxiety Index (STAI)⁵⁸. The STAI is one of the most used and cited measures of anxiety, with over 10,000 citations for Spielberger's two studies on the STAI^{58,59}. It has been used widely in radiotherapy settings. Short forms of the STAI have been investigated to create more clinically usable tools. These have been shown to perform well versus the full STAI^{60–62}. The STAI6 will be utilised here, as used by Marteau et al⁶⁰.

Anxiety will be measured at three timepoints:

- a. Baseline (after patient consent and enrolment on the trial)
- b. First treatment appointment, before treatment.
 - a. For patients on the intervention arm, this will be after the physicist consultation but before treatment
- c. End of treatment, before the last radiotherapy treatment

Scores range from 20 to 80, and a score of 40 is commonly used to differentiate between high and low anxiety⁶³. Scores at timepoints 1 & 2 will be corrected for baseline scoring for each participant, and the average (mean) score across both trial arms compared.

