8.2.2. Primary outcome

The primary outcome is the Spielberg state-trait anxiety index (STAI). Questionnaires that were not completed in the required timeframes will be treated as missing data:

- Baseline within 1 week of CT appointment
- Start of treatment on day of treatment
- End of treatment on day of treatment

Anxiety scores will be compared at each time point between the two groups for a statistically significant difference. The 2nd and 3rd timepoints will use baseline-corrected anxiety scores. Some additional analyses (including sensitivity analyses) on the primary outcome will also be conducted:

- a. The effectiveness of the intervention may vary across different subgroups of patients (e.g. age, education level). Therefore, supplementary statistical analyses are proposed in which it is tested if there is a statistical interaction between socio-demographic data and the primary outcome. This will include health literacy level measured at baseline.
- b. Any baseline variables that appear, by chance, to differ between the groups will be added in as covariates.
- c. Whether or not the patient has had previous radiotherapy will be added as a covariate.
- d. Longitudinal analysis of anxiety scores at all three time points to assess variation across treatment
- e. Proportions of high and low anxiety scores in each group at each time point.

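### Section 8.2 defines the analysis groups by receipt of the consultation, which conflicts with the arm-based wording elsewhere and would bias the primary comparison if receipt departs from allocation

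*Protocol*

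**What the plan says.** Section 8.2 sets the grouping for all the analyses that follow: "The pseudonymised data will be analysed by intervention group (i.e. patients who did or did not receive the additional consultation"). This is the only place where the protocol defines its analysis groups. Section 8.2.2 then applies the groups to the primary outcome without redefining them: "Anxiety scores will be compared at each time point between the two groups for a statistically significant difference".

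Other sections speak of randomised arms:

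- Section 6.3: "Participants will be allocated to intervention group or to the control group in a 1:1 ratio".
- Section 4.1, on the primary outcome: "the average (mean) score across both trial arms compared".
- Section 2.2.2 sets a secondary objective as a contrast between the intervention and control arms.
- Section 8.2.2(b) plans to adjust for baseline variables that differ between the groups by chance.

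Two statements in section 7.3 bear on whether receipt can differ from allocation. Medical physicist consultations are not part of standard care, "although they are done on an-hoc basis at a patients request". On timing: "The intervention will take place on the patients' first day of treatment, ideally face-to-face". Section 3.3 expects about two weeks between baseline and that day.

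**The concern.** Receipt is settled after randomisation and may be related to anxiety, which is the outcome. Under the literal wording, a participant allocated to the consultation who misses or declines it would be counted with the controls. A control participant who obtains an ad-hoc consultation could be counted with the intervention group, if that contact is classed as receipt. Either move breaks the comparability that randomisation provides. The resulting difference would mix the effect of the consultation with differences between the people who did and did not have one.

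The sentence states a rule. It does not leave the matter open, so a statistical analysis plan written to follow the protocol would carry the rule forward.

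**Working it through.** **Reproducing the plan's own figure.** Section 8.1 uses a difference of 10 points, SD 13, two-sided 5% significance and 80% power. The normal-approximation formula gives 27 per arm, 54 in total, and a 10% allowance raises this to 60. Both figures reproduce, so the point concerns the grouping and not the sample size arithmetic.

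**Setting the passages side by side.** Section 8.2 groups by receipt. Sections 2.2.2, 4.1 and 6.3 refer to arms or allocation. Section 8.2.2(b) presupposes randomised groups, because only there is a baseline difference due to chance alone. Both sets of statements can describe the same comparison only if nobody departs from allocation.

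**Size of the bias with no true effect.** Assumptions, none of which the protocol supplies:

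- A share *q* of participants would miss the consultation if allocated to it, taken as 10% or 20%.
- Their mean baseline-corrected score is *s* points higher than that of the others, taken as 5 or 10. This is a gap in change from baseline, not in baseline level.
- The SD of 13 from section 8.1 also applies to the baseline-corrected score.
- There are *n* = 27 evaluable participants per arm, and no control participant crosses over.

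Take the mean of those who would attend as 0. The received group then has mean 0 and size *n*(1-*q*). The not-received group holds *qn* participants from the intervention arm plus all *n* controls, of whom a share *q* are of the same type. Its mean is (*qns* + *qns*)/(*n* + *qn*) = 2*qs*/(1+*q*).

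Bias (received minus not received) = -2*qs*/(1+*q*).

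Standard error = 13 × √(1/[27(1-*q*)] + 1/[27(1+*q*)]):

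- *q* = 10%: 13 × √(1/24.3 + 1/29.7) = 3.56
- *q* = 20%: 13 × √(1/21.6 + 1/32.4) = 3.61

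Type I error = P(|Z + bias/SE| > 1.96):

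| *q* | *s* | Bias (points) | Bias/SE | Type I error |
|---|---|---|---|---|
| 10% | 5 | -0.9 | -0.26 | 5.8% |
| 10% | 10 | -1.8 | -0.51 | 8.0% |
| 20% | 5 | -1.7 | -0.46 | 7.5% |
| 20% | 10 | -3.3 | -0.92 | 15.2% |

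**Check by simulation.** This used 40,000 null trials per scenario, 30 per arm and a t-test. The as-received bias was -0.9, -1.8, -1.7 and -3.4 points, with type I error 5.7%, 7.6%, 7.5% and 14.5%. The same data analysed by randomised arm gave 4.0% to 4.7%. At 30 per arm, *q* = 10% is three participants.

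**Effect of the baseline correction.** If a share *k* of the gap is already present at baseline, a change score removes it and the bias becomes -2*qs*(1-*k*)/(1+*q*). With *s* = 10 and *k* = 0.5 (assumed), the results are those of the *s* = 5 rows. With *k* = 1 the bias is zero.

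If those who miss the consultation have lower baseline-corrected scores than the others, the sign reverses.

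**The case against.** The strongest reply is that the parenthesis in section 8.2 is loose shorthand for the arms. Section 6.3 uses the term intervention group for allocation, section 4.1 compares trial arms, and section 8.2.2(b) makes sense only for randomised groups. Section 4.3.1 uses similar receipt-based shorthand. This reading is plausible, and it is why the passages need reconciling. It does not make the sentence correct, because section 8.2 is the only definition given and its wording is explicit.

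A second reply is that a detailed statistical analysis plan is promised. That disposes of any complaint that the protocol omits a rule for non-adherence or the term intention to treat. It does not dispose of a grouping rule that the protocol states.

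A third is that departures may be few. Staff "will ensure the allocation is followed as described below"; the consultation falls on a routine visit day, is booked with a reminder where possible, and has a virtual fallback. Section 3.2 also expects participants who want information: "Participant selection bias will be present, with those patients wanting to know more self-selecting". These points make non-receipt less likely, but none of them says how a participant who departs from allocation is to be analysed.

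A fourth concerns the control arm. Ad-hoc consultations are outside standard care, and nothing says that one would count as the additional consultation. This stands: control crossover is possible but conditional, and it is not in the figures above.

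A reader might infer that the trial has given up the protection of randomisation outright, or that its result could not be attributed to the offer of a consultation. The documents do not support either. Any loss depends on departures from allocation whose rate is not given, and the largest bias illustrated is a third of the 10-point target (3.3/10). A reader might also carry a difference in anxiety level straight into the bias, but sections 4.1 and 8.2.2 use baseline-corrected scores at follow-up, so only a gap in change counts.

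**Conclusion.** The point holds in conditional form. Section 8.2 as written prescribes an as-received grouping and contradicts the arm-based wording of sections 4.1, 6.3 and 8.2.2(b). With full adherence the consequence is nil. With 10% to 20% non-receipt in the intervention arm and a gap of 5 to 10 points in baseline-corrected score, the null bias runs from about -0.9 to -3.3 points. Type I error then runs from just under 6% to about 15%. These sizes rest on assumed values of *q* and *s* and on SD 13 for the baseline-corrected score. They show what the wording could allow and do not predict what this trial will see. The sentence should be corrected before any analysis, because it governs the primary comparison.

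**What to change.** Reconcile the passages by replacing the parenthesis in section 8.2 with: *participants will be analysed in the arm to which they were randomised, whether or not a consultation took place.* Then:

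- Describe the analysis set as as-randomised with available outcome data. Restricting to those with outcome data does not by itself amount to a full intention-to-treat analysis unless missing data are also handled.
- Report, by arm, the number of allocated consultations not received and the number of ad-hoc consultations.
- Keep any received/not-received comparison only as a labelled supplementary analysis.

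The cost is one sentence in the protocol, carried into the statistical analysis plan, and a record of ad-hoc consultations among controls. Participants have no extra burden.

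One consequence should be accepted knowingly: analysis by arm estimates the effect of being allocated a consultation, which non-receipt dilutes. If those who miss it gain nothing, 10% non-receipt turns a 10-point effect into 10 × 0.9 = 9 points. Power with 27 evaluable per arm (t-test) then falls from 79% to 70%. The 10% over-recruitment in section 8.1 is for non-response, missing data and attrition, and does not cover this.
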